## **Introduction/background**

Influenza and pneumonia are the most common infection-related and vaccine-preventable causes of hospitalization and death. 90% of influenza-related deaths occur among adults aged >65 years. Over 2 million Americans reside in nursing homes, skilled nursing facilities, or long term residential care facilities and this number is expected to expand significantly in the coming decades according to the CDC. These are among the highest risk and debilitated seniors that may acquire influenza. Two influenza vaccines are now available that are FDA approved specifically for persons over age 65: the newly approved adjuvanted seasonal influenza vaccine (Fluad) and the high dose (HD) vaccine that was approved in 2009 and is increasingly being used. The absolute or relative clinical advantage to long-term care residents of Fluad vs. HD over standard dose (SD) vaccine remains unclear from existing immunologic and clinical evidence.

For Year 2, we will be adding a 3rd vaccine substudy, recombinant FLUBLOK. FLUBLOK is a newer FDA approved influenza vaccine that has a higher amount of HA in the formulation than SD, and has a unique feature of not being produced in eggs. None of the three vaccines have been compared head-to-head and an industry-sponsored study is unlikely to be conducted to evaluate relative efficacy or effectiveness due to uncertainty as to whether manufacturers will gain additional market advantage while risking uncovering relative inferiority.

Both Fluad, HD, and FLUBLOK vaccine have been shown to be more effective than SD vaccine in trials conducted in different cohorts. HD vaccine and FLUBLOK are more expensive than SD vaccine, and Fluad is less expensive than HD vaccine. As an adjuvanted vaccine, Fluad has been shown to have higher levels of heterologous immunity to drifted influenza strains than non-adjuvanted (SD) vaccine - another potential advantage of Fluad over HD vaccine, which is non-adjuvanted. This project's rationale and innovation derive from its ability to determine the best use of these two vaccines in the setting of one of the most vulnerable elderly populations - those living in nursing homes (NH) and other various long-term care institutions.

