### **Recruitment for the FLUBLOK pilot arm for Year 2:**

Any long term care facilities that participated on Year 1 of the study can participate on Year 2, as long as we do not repeat subjects. For the FLUBLOK substudy, we can recruit from those subjects that participated in Year 1 and received either the adjuvanted Fluvad or the HD Fluzone. Since enrolled subjects from Year 1 cannot participate for a 2nd year on the Fluvad vs. HD objective, these previously enrolled subjects would be eligible for recruitment on the FLUBLOK substudy, and therefore, we will use our previously described screening and recruitment methods to consent these subjects for enrollment to receive the FLUBLOK vaccine. We will consent these subjects on a separate FLUBLOK ICF. We may also recruit FLUBLOK subjects from new long term care facility sites that did not previously participate on the study, and we will use the same previously described consenting methods, and consent with the FLUBLOK ICF. If we hit our recruitment goals on the primary endpoint (Fluvad vs HD Fluzone objective), then any additional long term care residents that we may recruit will not be randomized to receive Fluvad or HD Fluzone, but rather will be enrolled in the pilot Aim 4 FLUBLOK arm. These residents will be consented on another ICF, that was modified specifically for FLUBLOK.

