### **Study procedures**

The intervention is randomization to one of the two FDA approved seasonal influenza vaccines (Fluad(AD) and FLUZONE HD (HD)) at 1:1 ratio. The HD vaccine will serve as the control, and the newly FDA-approved AD will be the comparator. We will obtain 20 ml of blood up to 2 weeks prior to the vaccine, or right before the vaccine is given. The second blood draw will be 4 weeks +/- 3 working days post vaccine and the third blood draw of 10 ml will be performed 2-4 weeks after the influenza season is over. The post-season draw may be spread over a two week window because the entire cohort of subjects will need to be drawn during this window, and it may take as long as two weeks to achieve that at all the facilities.

For the FLUBLOK substudy, we will follow the same blood draws and schedule. The subjects recruited to receive the FLUBLOK vaccine will be recruited with the FLUBLOK ICF, and will not be part of the randomization process.

The study will obtain blood work and give a study flu vaccine to consented residents starting in late September, and the third and last blood work will be obtained at the end of the flu season, typically in April. Each subject will then be enrolled as long as 8 months if they are enrolled in September and the flu season lasts until April.

We will obtain the following PHI in the prescreening: name, birthdate, race, ethnicity, gender, facility name and resident location, and whether a resident can self-consent or needs to use the LAR method of consenting. If a resident cannot self-consent, we will obtain the name, mailing address, phone numbers, and relationship of an LAR. We may also collect contact information on a secondary contact/secondary LAR, when appropriate, during the pre-screening process. Some residents may have two LARs/POAs listed in the medical record.

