### **Participant Enrollment and Follow-Up**

We will enroll 620 subjects over the 2 seasons of recruitment and enrollment. To minimize withdrawal from the study, recruiters will aim to identify subjects who have a high likelihood of still being a LTC resident present in the same facility for the second blood draw. This will be an important criterion for inclusion into the study. This is generally the case with LTC residents because length of stay is on the time scale of months to years rather than days to weeks.

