### **Analysis Plan**

The FDA guidelines (listed above) for demonstrating non-inferiority for a seasonal flu vaccine dictate the analysis of the co-primary endpoints. The ratio of the geometric mean titers will be assessed using tests of means on the log-transformed titers. The upper limit of the 95% CI of the difference (HD – Fluad) in the mean log titer will be compared to  $\log(1.5)$ . The difference in the seroconversion rates will be assessed with a two-sample proportion test. The upper limit of the 95% CI of the difference (HD – Fluad) in the seroconversion rates will be compared to 0.1. These analyses will be performed on HAI titers of all three strains obtained from studies of pre- and post vaccination serum.

For practical recruitment purposes we have to run the study over 2 years to recruit sufficient numbers of the full cohort for A/H3N2 analysis based on the sample size calculation. At the conclusion of our study, we can summarize the A/H3N2 HAI titers and seroconversion for each year separately; but our non-inferiority hypothesis is powered based on combining the years to include the total enrolment for the A/H3N2 analysis. Since we will recruit enough subjects each year due to small number of subjects needed to power the A/H1N1 analysis, we will perform and report separate analysis for each year studied as well as combining the data. For the B strain we are underpowered and will combine the two years for this exploratory result.

We will perform analyses on the other assays (NAI and SVN) on samples obtained at pre- and post- vaccination from all 3 strains. We will run HAI on all 3 strains for the post-season blood draw for Aim 1 as a secondary analysis for differences in the ability of titers to hold in one vaccine vs. the other for the length of the season. We will also run the NAI on the A/H3N2 only (for feasibility to keep assay number reasonable) on the post-season sample to assess if there are differences in maintaining anti-NA titers between the two vaccines. Any statistical tests performed for these assays are not powered to detect superiority or non-inferiority while preserving our study-wise error rate and will be considered exploratory in nature.

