Blood draws will be analyzed for humoral and cell mediated immune assays to determine flu-specific cells and antibody titers and immune status. Cells may be analyzed by RNAseq analysis to correlate aging immune responses and immune responses to the vaccines. We will not be making any DNA or doing any DNA gene analysis. No identifiable raw RNAseq files will be released that could be transcribed back to DNA for gene analysis purposes.

Analysis of FLUBLOK will be performed using the HAI and SVN assays as above and compared to the adjuvanted and high dose vaccines. NAI assays will not be used for this vaccine as it does not contain HA. If the pilot data are not powered by full non-inferiority studies we will also use Mann-U non-parametric tests to study differences in the mean responses between the vaccine groups.

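### Aim 4 compares a non-randomised, Year 2-only FLUBLOK arm with Fluad and HD groups enrolled over two seasons, naming no comparator year and not adjusting for baseline titer

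*Combined protocol and SAP*

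**What the plan says.** All references are to the combined protocol and SAP.

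- *Introduction/background* adds, for Year 2, a third "vaccine substudy, recombinant FLUBLOK".
- *Study procedures* states that FLUBLOK subjects "will not be part of the randomization process". On sampling it says: "For the FLUBLOK substudy, we will follow the same blood draws and schedule".
- *Recruitment for the FLUBLOK pilot arm for Year 2* allows re-enrolment: "we can recruit from those subjects that participated in Year 1 and received either the adjuvanted Fluvad or the HD Fluzone". Those people may not re-enter the Fluad versus HD randomisation. FLUBLOK subjects may also come from new facilities, or be residents recruited once the main trial is full.
- *Participant Enrollment and Follow-Up*: "We will enroll 620 subjects over the 2 seasons of recruitment and enrollment".
- *Analysis Plan*, methods for Fluad versus HD: "The ratio of the geometric mean titers will be assessed using tests of means on the log-transformed titers", and "The difference in the seroconversion rates will be assessed with a two-sample proportion test". Years are combined for A/H3N2 (by-year summaries possible) and for B. A/H1N1 is analysed by year and combined.
- *Analysis Plan*, FLUBLOK: "Analysis of FLUBLOK will be performed using the HAI and SVN assays as above and compared to the adjuvanted and high dose vaccines". Mann-Whitney tests are added if the pilot data lack the power for full non-inferiority analyses. No comparator season and no covariate are named.

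**The concern.** The main trial can combine its years because Fluad and HD are randomised 1:1 throughout, so season is broadly balanced between those two arms. An arm that exists in one season only lacks that protection. If its comparators include Year 1 subjects, any difference in titers between seasons enters the vaccine contrast. The same person can also contribute a Year 1 record as a comparator and a Year 2 record under FLUBLOK, although the planned tests assume independent groups.

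Baseline is a separate problem and does not depend on how the years are handled. The recruitment rules allow FLUBLOK subjects to have received Fluad or HD in the trial a year earlier, whereas nobody randomised in Year 2 can have done so. Pre-vaccine titers may therefore differ systematically between groups, and the post-vaccination GMT comparison takes no account of them.

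The *Significance* section says strains change from year to year and values same-season data for Fluad versus HD. Aim 4 has no matching rule. Its stated purpose is to prepare later studies (*Sample Size Considerations*), so a season or baseline difference mistaken for a vaccine difference could be carried into their planning.

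**Working it through.** **1. Group sizes.** *Study design* gives 500 subjects randomised 1:1 and up to 120 for FLUBLOK. 500 + 120 = 620, which reproduces the stated total. That is 500/2 = 250 per comparator vaccine over both years. The documents give neither the split by year nor any FLUBLOK effect size or power figure.

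**2. Shift from pooling the comparator years.** Let *r* be the Year 1/Year 2 GMT ratio in the comparators and *p* the share of comparators from Year 1; both are assumptions. The pooled comparator GMT is then r^p = exp(p × ln r) times the Year 2 GMT, and the FLUBLOK/comparator ratio is off by that factor.

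| Season ratio r | p = 1/3 | p = 1/2 | p = 2/3 |
|---|---|---|---|
| 1.5 | 1.14 | 1.22 | 1.31 |
| 2 | 1.26 | 1.41 | 1.59 |

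If Year 1 titers are the higher, FLUBLOK looks worse: a true ratio of 1 is estimated as 1/1.22 = 0.82 or 1/1.41 = 0.71 at p = 1/2. If they are the lower, FLUBLOK looks better. With Year 2 comparators only, p = 0 and the factor is 1.

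**3. Shift against precision.** In SD units the pooled standard error is √(1/120 + 1/250) = 0.1111. The documents give no SD. An SD of 1.0 ln unit is assumed at the low end. At the high end, 1.595 is what the planned 243 per group implies for a margin of ln 1.5, 80% power and a true ratio of 1: 0.4055 × √(243/2) / (1.960 + 0.842). The 95% limits then lie a factor exp(1.96 × 0.1111 × SD) = 1.24 to 1.42 either side of the estimate. A shift of 1.22 is close to the lower of these.

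**4. Precision cost of Year 2 comparators** (independent groups, equal SD):

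| FLUBLOK n | Year 2 comparators per vaccine | SE, Year 2 only | SE, pooled | Ratio |
|---|---|---|---|---|
| 120 | 125 (half) | 0.1278 | 0.1111 | 1.15 |
| 120 | 167 (two thirds) | 0.1197 | 0.1111 | 1.08 |
| 120 | 83 (one third) | 0.1428 | 0.1111 | 1.29 |
| 60 | 125 (half) | 0.1571 | 0.1438 | 1.09 |

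**5. People in both groups.** With *k* people shared per comparator vaccine and within-person correlation ρ across years (both assumed), the pooled variance is 1/120 + 1/250 − 2kρ/(120 × 250).

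- k = 30, ρ = 0.5: SE 0.1065. An even-split Year 2 restriction then costs 0.1278/0.1065 = 1.20.
- k = 15, ρ = 0.3: cost 1.165.
- k = 60, ρ = 0.7: cost 1.309.

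**6. Baseline.** The documents give neither the baseline difference nor the pre-post correlation, so no size is claimed. *Sample Size Considerations* defines seroconversion relative to the pre-vaccine titer; the post-vaccination GMT has no such link.

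**The case against.** The strongest reply is that pooling is never stated. The year-combining rules are written for Fluad versus HD, and the FLUBLOK sentence's reference back may cover only the assays and tests. A same-year comparison is a natural reading of a substudy added for Year 2. This stands: the season and overlap problems are conditional on pooling. The missing comparator year and the missing baseline adjustment are not.

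Second, Aim 4 is an unpowered pilot with no decision rule of its own, and its non-randomised status can be read from *Study procedures*. By-year results are planned for A/H1N1 and possible for A/H3N2, so a reader could look at Year 2 comparators for both A strains. That limits the risk of misreading and keeps the point minor, but no by-year result is offered for B.

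Third, with positive within-person correlation, ignoring the overlap makes the reported standard error too large, not too small: 0.1111 against 0.1065, about 4%, and about 1% to 14% over the range in step 5. This is correct. The overlap breaks an assumption of the tests but does not by itself produce false positives.

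Fourth, the season ratios are assumed, and a real season difference would also inflate the pooled variance. With an SD of 1 ln unit and an even split, the cost of the restriction falls to about 14% at a ratio of 1.5 and 13% at 2. That slightly favours the fix.

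Finally, the fix leaves prior-year study vaccination unbalanced, and Year 2 comparators may not be fully concurrent if FLUBLOK enrolment starts after the main trial fills. Both remain as limits of a non-randomised comparison.

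**Conclusion.** The concern holds, at low severity. The plan sets a one-season, non-randomised arm against groups enrolled over two seasons, does not say which comparator year applies, and uses only unadjusted tests. The season bias arises only if comparators are pooled; its direction and size are unknown. Over assumed season ratios of 1.5 to 2 and Year 1 shares of one third to two thirds, the FLUBLOK GMT ratio shifts by a factor of 1.14 to 1.59. The lack of baseline adjustment applies on either reading, with no magnitude claimed. The randomised Fluad versus HD comparison is unaffected.

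**What to change.** For Aim 4, amend the *Analysis Plan* to:

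1. use as comparators only the Fluad and HD subjects enrolled in Year 2, so that no person's Year 1 record serves as a comparator;
2. compare post-vaccination log titers with adjustment for baseline log titer;
3. describe the result as a non-randomised pilot comparison.

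This changes wording only. The baseline sample is already collected, because FLUBLOK subjects follow the same blood-draw schedule.

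Against the standard error that the plan's two-sample tests would report for pooled groups, the price is about 15% with an even year split (8% to 29% if Year 2 holds two thirds to one third of comparators), or 9% with 60 FLUBLOK subjects. Against a pooled analysis that allowed correctly for people in both groups, it is about 20% (16% to 31%). Baseline adjustment would recover part of this, depending on a pre-post correlation that the documents do not give. Selection bias remains after these changes and should be acknowledged when the result is reported.
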